5.6.4 Completion/Final Evaluation

Visit 9 (36 months post-randomization) - Patients will return for evaluation of antihypertensive response to therapy according to randomized treatment group and will have final research testing for WMH, mobility, cognitive function as well as blood pressure control. Procedures previously defined above will be done at this visit:

- Medical history, concomitant medications, adverse events, medication compliance
- Standardized clinic BP measurements, body weight and height
- Antihypertensive medication will be prescribed/continued according to clinical goals for long-term management. Clinical follow-up will be arranged with either primary care physician, one of the study physicians, or both, depending on wishes of study patient.
- Safety laboratory studies (potassium, creatinine, BUN) if clinically necessary
- Electrocardiogram
- Ambulatory blood pressure monitoring
- MRI acquired at UCONN neuroradiology
- Mobility Testing
- Cognitive Testing
- Questionnaires related to urinary function, QOL

- Home BP monitoring

Early termination patients who complete at least 18 months of randomized therapy will be considered completed study patients and all comprehensive tests will be completed that were designated for visit 9.

SAFETY ASSESSMENTS

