6. INTERVENTION DISCONTINUATION

- A. Patients will be discontinued from their antihypertensive intervention if it is deemed that the treatment(s) or blood pressure level is no longer safe or appropriate based on clinical condition (e.g. development of congestive heart failure that mandates a specific regimen or development of a terminal malignancy).
- B. Potential reasons for discontinuation of the intensive treatment might include untoward symptoms associated with low blood pressure related to development of a new morbidity (e.g. blood loss, sepsis) or intolerance to therapy (e.g. lightheadedness/syncope. In rare cases, hyperkalemia or hyponatremia may develop that would be unmanageable under the constraints of the protocol-drive therapies. Hypokalemia will be managed with aggressive potassium replacement to maintain serum levels > 3.5 meq/L.
- C. As this is an intention-to-treat trial, patients who discontinue treatment interventions will be invited to participate in clinical follow-up and all comprehensive outcome studies at months 18 and 36 of the trial.
- D. In the event of temporary discontinuation of antihypertensive treatment (e.g. need to withhold antihypertensive medications due to surgery, post-operative bleeding, infection or other causes of low blood pressure), reassessment of these individual patients will be made

in the research clinic for a return of BP levels towards baseline, and study medications will then be resumed.

[figure not shown]

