8.2 Hypotheses and Statistical Analyses

The Figure shows graphically how our hypotheses relate to one another. Hypothesis 1 tests the combined effects of paths A, B, C, D & E i.e., the total effect of BP on mobility. Hypothesis 2 tests path A, Hypothesis 3 tests path D, Hypothesis 4 tests path B+E; together Hypotheses 2, 3 and 4 together test the effect of BP on mobility mediated through BP's effects on WMH and WM microstructure. Hypothesis 5 tests the relative importance of paths A and B to that of path C, i.e., the degree to which the effect of BP on mobility is explained by WMH. Hypothesis 6 tests the relative importance of paths D and E to that of path C, i.e., the degree to which the effect of BP on mobility is explained by changes in WM microstructure.

Hypothesis path diagram

Hypothesis 1: Intensively treating 24-h systolic BP to a goal of <130 mmHg versus standard BP control of <145 mmHg will lead to faster walking speeds at T₃₆. (Paths A&B+C+D&E)

Hypothesis 2: Intensively treating 24-h systolic BP to a goal of <130 mmHg versus standard BP

control <145 mmHg will lead to smaller total WMH volume. (Path A)

Hypothesis 3: Intensively treating 24-h systolic BP to a goal of <130 mmHg versus standard BP

control <145 mmHg will stabilize brain WM microstructural integrity (FA and MD) at T₃₆. (Path

D) We will perform 3 sets of analyses for hypotheses 1, 2 & 3:

- a. Multiple linear regression will be performed with treatment group (intensive vs. standard) as the predictor of interest. Gait velocity at T₃₆ is the primary outcome for hypothesis 1, WMH at T₃₆ is the primary outcome for hypothesis 2, and DTI indices (FA and MD) are the primary outcomes for hypothesis 3. The analysis will be intention-to-treat. Age, sex, and 24 hour SBP at T₀ (baseline) will be included as covariates, along with other demographic factors for which the treatment groups are not comparable. **The analysis for hypothesis 1 is the proposal's primary efficacy analysis and thus the proposal is powered to address this analysis (see Sample size estimation).**

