- b. We will repeat analyses 1a, 2a and 3a but with gait velocity at T₁₈, total WMH at T₁₈, and DTI indices at T₁₈ as the primary outcomes. A comparison of these analyses with analyses 1a and 1b will determine the time course of the intervention's effects. In particular, it will be important to determine if these effects occur early (T₁₈) or require a 3-year treatment period. In addition, for participants who are present at T₁₈ but not T₃₆, the data from T₁₈ will be used to estimate the effect of informative loss to follow-up. (See Missing Data)
- c. We will further examine the progression of mobility and WMH changes using a progression model using methods adapted from Diggle:³⁶

$$Y_{i0} = b_{i0} + \beta_T (X_i) + \text{cross sectional covariates} + \text{residual error}$$

$$Y_{i18} = b_{i0} + \beta_T (X_i) + \beta_L + \beta_E (X_i) + \text{cross sectional covariates} + \text{longitudinal covariates} + \text{residual error}$$

$$Y_{i36} = b_{i0} + \beta_T (X_i) + \beta_L^* + \beta_E^* (X_i) + \text{cross sectional covariates} + \text{longitudinal covariates} + \text{residual error}$$

Here, Y_{i0} , Y_{i18} , and Y_{i36} are the outcomes (mobility or imaging) at T_0 , T_{18} , and T_{36} for study participant i , and X_i is the treatment group assignment indicator for study participant i , and b_{i0} is a random intercept used to account for the fact that repeated measurements on individuals are not independent; the other β_j 's are fixed effects in this example although we will consider the possibility that treating them as random effects will add to the model fit. The model will be fit as a linear mixed model.^{37, 38} The parameters of interest are β_E , and β_E^* , the difference in the outcome progression rate (mobility or imaging) between the treatment groups at T_{18} and T_{36} . If the difference in the rate of progression is constant during follow-up, we would expect β_E^* to approximately equal $2 \times \beta_E$. This allows a more powerful and rigorous test of whether the intervention's effects are manifested quickly or over the long-term. Additional secondary analyses will use the T_{18} data to determine temporal continuity of the trends and as a partial assessment of the effect of dropout. Additional secondary analyses will use logistic regression with severity of urinary incontinence at T_{36} and T_{18} as an ordinal outcome.

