Product of coefficients methods^{35,36} will be used for formal statistical inference regarding the mediation. Specifically, we will estimate the product of the effect estimated for hypothesis 2 corresponding to Path A (the effect of intervention group on total WMH at T₃₆), and the effect estimated for hypothesis 3 corresponding to Path B (the effect of WMH at T₃₆ on gait velocity at T₃₆). The magnitude of this product turns out to be proportional to the change in the effect of intervention group on gait velocity at T₃₆ when WMH at T₃₆ is added to a regression model of gait velocity at T₃₆ as a function of intervention group. Similar models will be used to assess outcomes at T₁₈, and the cognitive outcomes. As formal tests for mediation using the product of coefficients method require larger sample sizes than available in this study, we will treat results from analyses in Hypothesis 5 as preliminary, to be potentially verified by a larger study should the main effects in Hypotheses 1-3 be confirmed.

Hypothesis 6: Diffusion tensor imaging (DTI) indices (FA, MD) at T₀ and at T₃₆ mediate the effect of treatment group, showing that the mechanism by which reduced ABP is linked to better mobility occurs by preserving brain WM microstructural integrity (FA, MD).

(Paths C – D&E) The same analysis as used for hypothesis 5, except that the mediating effect of the DTI indices will be assessed.

Missing Data.

Death and study attrition are associated with age-related diseases. Failure to account for this informative censoring may result in biased estimates of dementia risk and cognitive decline.³⁷ Hence, we will collect data by telephone to assess the degree to which living participants who fail to appear for their final assessment differ from participants who complete the study. As mentioned above, we will use telephone administration of a validated mobility assessment³⁹ and the method developed by [name] and colleague³⁰ to estimate mobility outcomes through multiple imputation or joint modeling that would have been

observed had the participants appeared for their clinical assessment. While our primary efficacy outcome analysis will be limited to participants who complete the study, this will be the first trial in aging with the potential to assess the impact of informative dropout beyond usual sensitivity analyses.

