Here, x_i is the treatment group indicator for participant i (one for intervention, zero for comparison); Y_{i1} is the WMH % for participant i at time 1 (baseline); Y_{i2} is the WMH % for participant i at time 2 (36 month follow-up); β_0 is interpreted as the average WMH % at baseline in the reference group; β_C is interpreted as the difference in the average WMH % at baseline between the intervention group and the reference group and will be zero if the two groups are exactly comparable in their baseline values; β_L is interpreted as the average change in WMH % between 36 month follow up and baseline in the reference group; β_T is interpreted as the difference average change in WMH % between 36 month follow up and baseline between the intervention group and the reference group and thus the parameter of primary interest; γ_i is a random intercept for participant i that addresses the correlation in WMH % across the two time points; and ε_{i1} and ε_{i2} are the residual error terms at baseline and follow-up, respectively. All analyses will be repeated as stratified analyses (b - e below).

- b. Stratified according to < or > median age
- c. Stratified according to gender
- d. Stratified according to median years of education
- e. Stratified according to a clinical diagnosis of minor or major depression
- f. Stratified according to presence or absence of statin therapy for hyperlipidemia
- g. Stratified according to presence or absence of anti-platelet therapies (aspirin, clopidigrel)
- h. Sensitivity analysis at 36 months by ambulatory systolic BP : rationale – for study patients who either never met the achieved BP for their group assignment or who shifted mid-trial to an ambulatory BP

value out of alignment with their assigned treatment group (e.g. a standard group patient whose 24 hour systolic BP was < 135 mmHg would be excluded from the sensitivity analysis; an intensive group patient whose 24 hour systolic BP was > 135 mmHg would be excluded from the sensitivity analysis).

2. Change in mobility, cognition and depression from baseline to 3 years
 - a. According to treatment group (primary analysis)

$$Y_{i1} = \beta_0 + \beta_C x_i + \gamma_i + \varepsilon_{i1}$$

$$Y_{i2} = \beta_0 + \beta_C x_i + \beta_L + \beta_T x_i + \gamma_i + \varepsilon_{i2}$$

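### Protocol 5.6.4 lets patients who leave after month 18 count as completed on an undated Visit 9 battery, so tests from months 18 to 35 can enter the analysis as 36-month outcomes

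*Protocol*

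**What the plan says.** - **Protocol 5.6.4 (Completion/Final Evaluation).** "Early termination patients who complete at least 18 months of randomized therapy will be considered completed study patients", and for them "all comprehensive tests will be completed that were designated for visit 9". Visit 9 is the month-36 visit. No date is given for the early battery, and no rule for storing or analysing it.
- **Protocol 6.C (Intervention Discontinuation).** "patients who discontinue treatment interventions will be invited to participate in clinical follow-up and all comprehensive outcome studies at months 18 and 36".
- **Protocol 8.2 (Hypotheses and Statistical Analyses), analysis a.** "Gait velocity at T₃₆ is the primary outcome for hypothesis 1". WMH and the DTI indices at month 36 are handled in the same way.
- **Protocol 8.2, Missing Data.** "our primary efficacy outcome analysis will be limited to participants who complete the study".
- **Protocol 8.2, analysis b.** For patients seen at month 18 but not at month 36, the month-18 data "will be used to estimate the effect of informative loss to follow-up".
- **SAP items 1 to 5.** Two fixed occasions, baseline and 36 months. In item 1 the time coefficient "is interpreted as the average change in WMH % between 36 month follow up and baseline in the reference group". No window is set and no term represents the month in which a test was done.
- **Protocol 4.3.** The 140 planned completers are patients with 3 years of randomised treatment, which is not the 18-month standard of 5.6.4.

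**The concern.** The question is when the outcome is measured. A patient who stops at month 20 may have the final battery soon afterwards under 5.6.4, or at month 36 under 6.C. If the first happens, 5.6.4 makes the patient a completer, the primary analysis takes completers, and the models know only one follow-up time. Following the stated rules can therefore put about 20 months of change into a 36-month estimate.

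This matters because the protocol itself describes mobility loss linked to WMH as gradual (2.2 and 8.3). Three things are at stake:

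- the size of the 36-month estimate;
- the comparison of month-18 and month-36 effects in 8.2 b and c, which is meant to show whether the benefit comes early or needs three years;
- the dropout check in 8.2 b, which relies on patients with a month-18 but no month-36 assessment. A late leaver credited with a Visit 9 battery could fall outside that group.

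**Working it through.** **1. The plan's own figures.** Protocol 8.3 gives 140 completers, covariate r² of 0.1267, and 85% power for an increase of 0.0533 to 0.1800. Alpha is not stated; I assume 0.05. For a partial F test of one added predictor over three covariates:

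- noncentrality = 140 × 0.0533 / (1 − 0.1800) = 9.10, with 1 and 135 degrees of freedom; power = 0.850. The stated figure reproduces.
- 140 / (1 − 0.30) = 200 randomised, as stated.

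**2. Share of 36-month change captured.** Assume linear change, 70 patients per arm tested at month 36, and n late leavers per arm tested on average at month m. The share captured is (70 + n × m/36) / (70 + n). The documents give neither n nor m. With about 30 of 100 patients lost per arm, n cannot exceed about 30, and deaths and departures before month 18 lower it further.

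| Late leavers (intensive / standard) | Mean test month | Intensive | Standard | Gap |
|---|---|---|---|---|
| 15 / 15 | 27 | 81.25/85 = 0.956 | 0.956 | 0; both diluted 4.4% |
| 20 / 10 | 27 | 85/90 = 0.944 | 77.5/80 = 0.969 | 0.024 |
| 20 / 10 | 18 | 80/90 = 0.889 | 75/80 = 0.938 | 0.049 |

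The gap is a share of 36-month progression, not of the treatment effect. Swapping the arms reverses its sign.

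**3. In gait-speed units.** The prior cohort's 0.15 m/sec went with an r² increase of 0.1082. With balanced arms and treatment unrelated to the covariates, the design increase corresponds to 0.15 × √(0.0533/0.1082) = 0.105 m/sec. Assume a decline of 0.05 to 0.20 m/sec over 36 months.

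- Gap of 0.024: 0.001 to 0.005 m/sec, about 1% to 5% of 0.105.
- Gap of 0.049: 0.002 to 0.010 m/sec, about 2% to 9% of 0.105.

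**4. Power under dilution.** This depends on whether late leavers are part of the 140 or come on top of them.

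- *Part of the 140.* If a share s of both arms is tested at mean month m, the effect is multiplied by 1 − s(36 − m)/36 and the r² increase by its square. For s = 10% and m = 30 the factor is 0.983 and power 0.84. For s = 30% and m = 18 the factor is 0.85 and power 0.71.
- *On top of the 140* (15 per arm, month 27, N = 170). The r² increase is 0.0533 × 0.956² = 0.0487, and noncentrality = 170 × 0.0487 / (1 − 0.1267 − 0.0487) = 10.0, above 9.10. Power does not fall below plan, but the estimate is still 4.4% too small as a 36-month effect.

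**5. Time-course comparison.** Protocol 8.2 c expects the month-36 effect to be about twice the month-18 effect if the difference in progression rate is constant. With the factor 0.956 the expected ratio is 2 × 0.956 = 1.91, a small pull towards an apparently early effect.

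**The case against.** The strongest reply is that the two sections may cover different patients. Section 5.6.4 speaks of early termination, which can mean leaving the study; 6.C speaks of stopping the intervention while remaining in follow-up. An exit battery for leavers is compatible with month-36 tests for those who stay. That may be the intention, so a flat contradiction is not proven. But the documents never draw the line. And if they did, a true leaver's battery would have to come before month 36, which leaves the analysis problem in place.

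Second, 5.6.4 does not say that the tests are done at the moment of stopping or stored as month-36 values. Read literally, a month-20 result is not a month-36 outcome, and the patient stays in the 8.2 b dropout group. This is correct, which is why the finding is that such values can enter. What makes it more than missing detail is the stated combination of completed status and a completers-only primary analysis, with no window to keep early tests out.

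A reader might also infer that the rule flatters intensive treatment, since 6.B names symptoms of low pressure as a possible reason to stop it. The documents do not support that. Those patients discontinue treatment and so fall under the month-36 invitation in 6.C; 6.B gives no rates by arm; and patients who leave because they are ill may test worse, which reverses the sign. Practice effects from a battery repeated soon after month 18 are likewise possible, but no text establishes such an interval.

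Finally, the plan has some protection: Missing Data describes telephone mobility assessment with imputation or joint modelling. It is aimed at living participants who fail to appear for the final assessment, so a late leaver who has already had the Visit 9 battery may not be included.

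**Conclusion.** The concern holds as a mistiming and dilution risk. The stated rules allow tests from months 18 to 35 to be analysed as 36-month outcomes, and the sections do not say which testing rule applies to a patient who stops between months 18 and 36.

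The likely size is modest: about 4% dilution with equal late leaving, and about 2% to 5% of 36-month progression with a 20 versus 10 split, in either direction. These figures rest on linear change, on leavers who resemble stayers, and on assumed numbers and test months. A loss of power follows only if late leavers make up part of the 140. The effect on the dropout check cannot be quantified from the documents, but it touches the analysis meant to show whether loss to follow-up is informative.

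**What to change.** 1. Reconcile 5.6.4 with 6.C: state which patients each covers, when each is tested, and what completed means for the primary analysis.
2. Label any battery done at early termination as an early-termination assessment, with its actual date.
3. Keep the month-36 invitation for every patient still willing to attend.
4. State a window around month 36 and count only tests inside it as month-36 outcomes in 8.2 a and SAP items 1 to 5.
5. Use earlier tests at their actual month since randomisation in the mixed model.
6. Define the 8.2 b dropout group as patients with no test inside the window.

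The cost is protocol and SAP wording, one visit label and one date field. Treatment is unchanged. The drawback is that the reported number of month-36 completers may be slightly lower.

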5.7 Specification of Safety Parameters

There are no experimental antihypertensive drugs in the trial. All medications that will be used are quite mature and have been in clinical use for > 15 years. Due to the age of the study patients, a number of serious and non-serious adverse events are expected and will be tabulated according to treatment assignment. Should a study patient have symptoms suggestive of vertebrobasilar insufficiency, whether prior to enrollment or during follow-up, the patient will be evaluated by a neurologist. All discontinuations due to serious and non-serious adverse events will be tabulated according to treatment assignment as well. These include:

Serious Adverse Events

- Major adverse cardiovascular events: cardiovascular death, nonfatal myocardial infarction, nonfatal stroke, unstable angina with urgent revascularization.
- Cardiac arrhythmias not associated with ischemia
- Hospitalized congestive heart failure
- Falls and/or syncope associated with injury (e.g fractures)
- Non-cardiovascular death
- Venous thromboembolic events (pulmonary embolism, deep venous thrombosis)
- Aortic aneurysm rupture, surgery
- Peripheral arterial surgery
- Coronary and peripheral revascularization, elective
- Major life-threatening infections

Non-Serious Adverse Events

- Potential symptoms/signs of low systolic BP (recorded systolic BP < 90 mmHg, postural reduction in systolic BP > 20 mmHg, lightheadedness, near syncope, falls without injury)
- Non-serious or non-severe adverse events according to body system: allergic, hematologic, gastrointestinal, pulmonary, renal, etc.)

Safety laboratory parameters

The key safety laboratory studies in the trial will include: hematocrit, potassium, sodium, creatinine, blood urea nitrogen, glucose, and AST. Each laboratory parameter will be evaluated in context of the individual patient. In general, large changes (e.g. doubling of serum creatinine) will be evaluated immediately, whereas small changes (e.g. a 15% increase in serum creatinine from baseline) will be repeated in a convenient fashion for the patient. Potassium supplements will be prescribed as needed.

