5.5 Schedule of Evaluations

Assessment during the randomized clinical trial of intensive versus standard ambulatory BP control

	Screen	Baseline		R A N D O M I Z E D	MONTH								Post Study	
		I	II		1	2	3	6	12	18	24	30		36
Med Hx-Phys Ex	X				X					X			X	
Med Washout (0 to 4 week period)		X	X											
ECG	X					PRN*	PRN	PRN	PRN	X	PRN	PRN	X	
CBC, Chemistries		X				PRN	PRN	X	X	X	X	PRN	X	
MRI	X									X			X	
Gait/Mobility			X							X			X	
Cognitive Tests			X							X			X	
Urinary Function		X								X			X	
Clinic BP,HR,BMI	X	X	X		X	X	X	X	X	X	X	X	X	X
Med Titration					X	X	PRN	X	PRN	PRN	PRN	PRN		
Adverse Events			X		X	X	X	X	X	X	X	X	X	X
ABPM (24hr)			X				X	X**		X			X	
HOME BP			X						X	X	X	X	X	

*PRN laboratory testing for safety checks only (electrolytes, and renal function tests); note: due to the age of patients, medical staff and PIs will be available at all times for impromptu visits; ** - if needed based on 3 month ABPM and/or changes in clinic BP

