- Ambulatory blood pressure monitoring if clinic systolic BP has been stable for visits 2 and 3 according to treatment assignment. If not, patients will return in 2-4 weeks for re-assessment of BP stability. Antihypertensive drug titration will be based on ambulatory BP from this point forward.
- Dispense medications for next 3 months

Visit 4 (6 months post-randomization) – Patients will return for evaluation of antihypertensive response to therapy according to randomized treatment group. Procedures previously defined above will be done at this visit:

- Medical history, concomitant medications, adverse events, medication compliance
- Standardized clinic BP measurements, body weight and height
- Antihypertensive medication titration or down-titration as appropriate – ad hoc ambulatory BP can be performed here to address therapeutic goals and if deemed medically necessary.
- Safety laboratory studies (potassium, creatinine, BUN) if clinically necessary

- Electrocardiogram if clinically necessary
- Dispense medications for next 6 months

Visit 5 (12 months post-randomization) – Patients will return for evaluation of antihypertensive response to therapy according to randomized treatment group. Procedures previously defined above will be done at this visit:

- Medical history, concomitant medications, adverse events, medication compliance
- Standardized clinic BP measurements, body weight and height
- Antihypertensive medication titration or down-titration as appropriate; ad hoc ambulatory BP can be performed here to address therapeutic goals and if deemed medically necessary.
- Laboratory studies (potassium, creatinine, BUN, glucose, ALT, cholesterol profile)
- Electrocardiogram if clinically necessary
- Home BP monitoring
- Dispense medications for next 6 months

Visit 6 (18 months post-randomization) – Patients will return for evaluation of antihypertensive response to therapy according to randomized treatment group and will have comprehensive testing for WMH, mobility, cognitive function as well as blood pressure control. Procedures previously defined above will be done at this visit:

- Medical history, concomitant medications, adverse events, medication compliance
- Standardized clinic BP measurements, body weight and height
- Antihypertensive medication titration or down-titration as appropriate; ambulatory BP will be performed to evaluate achievement of therapeutic goals according to randomized treatment strategy.

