- Safety laboratory studies (potassium, creatinine, BUN) if clinically necessary

- Electrocardiogram
- MRI acquisition at UCONN neuroradiology
- Mobility Testing
- Cognitive Testing
- Questionnaires related to urinary function, QOL
- Home BP monitoring
- Dispense medications for next 6 months

Visit 7 (24 months post-randomization) – Patients will return for evaluation of antihypertensive response to therapy according to randomized treatment group. Procedures previously defined above will be done at this visit:

- Medical history, concomitant medications, adverse events, medication compliance
- Standardized clinic BP measurements, body weight and height
- Antihypertensive medication titration or down-titration as appropriate; ad hoc ambulatory BP can be performed here to address therapeutic goals and/or if deemed medically necessary.
- Safety laboratory studies (potassium, creatinine, BUN) if clinically necessary
- Electrocardiogram if clinically necessary
- Home BP monitoring
- Dispense medications for next 6 months

Visit 8 (30 months post-randomization) – Patients will return for evaluation of antihypertensive response to therapy according to randomized treatment group. Procedures previously defined above will be done at this visit:

- Medical history, concomitant medications, adverse events, medication compliance
- Standardized clinic BP measurements, body weight and height

- Antihypertensive medication titration or down-titration as appropriate; ad hoc ambulatory BP can be performed here to address therapeutic goals and/or if deemed medically necessary.
- Safety laboratory studies (potassium, creatinine, BUN) if clinically necessary
- Electrocardiogram if clinically necessary
- Home BP monitoring
- Dispense medications for next 6 months

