For mobility, cognition, and depression, variables are defined as in (1) with the following additions: δ_i is residual error in the model for change in WMH, and m_{i1} and m_{i2} are the values of WMH at baseline and follow-up, respectively. Some mediation measures of interest are as follows:

$$CDE = \beta_T$$

$$INT_{REF} = \theta_{INT} \alpha_0$$

$$INT_{MED} = \theta_{INT} \alpha_1$$

$$PIE = \theta_M \alpha_1$$

The controlled direct effect $CDE = \beta_T$ is the effect of treatment assignment in the absence of any WMH, $INT_{REF} = \theta_{INT} \alpha_0$ is the reference interaction between treatment assignment and WMH, $INT_{MED} = \theta_{INT} \alpha_1$ is the mediated interaction, and $PIE = \theta_M \alpha_1 x_i$ is the pure indirect effect. Combinations of these derived measures will be used to assess the degree of mediation, as described in VanderWeele. T.J. (2015). Explanation in Causal Inference: Methods for Mediation and Interaction, Oxford University Press. In particular, the proportion mediated is $\frac{INT_{REF} + INT_{MED} + PIE}{CDE + INT_{REF} + INT_{MED} + PIE}$.

Bootstrap standard errors and confidence intervals will be used for statistical inference, including estimation of standard errors and confidence intervals.

In secondary analyses, age, sex, and resultant ambulatory systolic BP at 36 months regardless of treatment assignment will be considered as mediators through similar methods. Specifically, age, sex, and systolic BP will replace $m_{i2} - m_{i1}$ in the model above and similar measures of interaction and mediation will be estimated.

7. Special Interest adverse events (falls, nervous system and vascular disorders) as related to numerous predictors of interest.

These outcomes are all count variables, so we use Poisson regression with each of the following predictors.

$$\log(\mu_i) = \log(n_i) + \beta_0 + \beta_1 x_i$$

Here μ_i is the count, n_i is the number of months in study, β_0 is the intercept with $\exp(\beta_0)$ interpreted as the rate of AE with mobility scale is zero, x_i is the predictor of interest, mobility scale and β_1 is the log rate ratio between groups and $\exp(\beta_1)$ is interpreted as the estimated ratio of rates for two subjects differing by one in their predictors of interest scale. This analysis will be repeated for the following predictors described below:

- a. Mobility variables
- b. Cognitive variables
- c. Treatment assignment
- d. Blood pressure
- e. Age
- f. Gender

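### Creatinine, potassium and sodium are named as key safety tests, but no planned analysis compares their values between the arms

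*Protocol*

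**What the plan says.** Protocol 5.7 lists the key safety laboratory tests as "hematocrit, potassium, sodium, creatinine, blood urea nitrogen, glucose, and AST". On their use it says that "Each laboratory parameter will be evaluated in context of the individual patient". It then gives examples of how quickly a result is followed up: a doubling of creatinine at once, and "a 15% increase in serum creatinine from baseline", described as a small change, at the patient's convenience. Protocol 6 recognises the electrolyte risk: "In rare cases, hyperkalemia or hyponatremia may develop that would be unmanageable under the constraints of the protocol-drive therapies".

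The by-arm safety output in the Protocol is a tabulation of adverse events and of discontinuations due to them (5.7). Under 5.9 the safety committee receives aggregate reports every four months that include laboratory data; a split by arm is not stated. Section 5.8 has the analysis of safety parameters in its title but contains no laboratory analysis, and neither does the statistical section. The SAP has one safety item, item 7: "Special Interest adverse events (falls, nervous system and vascular disorders) as related to numerous predictors of interest".

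On collection, the table in 5.5 marks chemistries as fixed at Baseline I and at months 6, 12, 18, 24 and 36, and as needed at months 2, 3 and 30. The visit text in 5.6.3 and 5.6.4 makes potassium, creatinine and BUN unconditional at month 12 only. At months 2, 3, 6, 18, 24, 30 and 36 it reads "Safety laboratory studies (potassium, creatinine, BUN) if clinically necessary".

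**The concern.** Renal and electrolyte effects are harms that the protocol itself foresees in people aged 75 and over, and a laboratory value measures them without judgement. Followed as written, the plan uses that value for individual care and committee oversight but not for comparing the arms. The comparison is left to recorded adverse events.

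This matters because the trial is open label. The treatment assignment section states that clinical staff and investigators know the assignment; only those who perform the outcome tests are blinded. No laboratory threshold defines an adverse event. Whether a shift in creatinine or potassium becomes one is therefore partly a judgement made with knowledge of the arm. Incomplete recording can hide a real excess, and recording that differs by arm can produce an apparent one. Either could distort the balance of harm against any mobility benefit.

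**Working it through.** **1. Where the laboratory values are used.**

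- Protocol 5.7: individual patient evaluation.
- Protocol 5.9: aggregate reports to the safety committee.
- Protocol statistical section: no laboratory variable.
- SAP items 1 to 6: imaging, mobility, cognition, depression, urinary function, sleep, quality of life and mediation.
- SAP item 7: counts of falls, nervous system and vascular events. No renal, electrolyte or laboratory variable appears as outcome or predictor.

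No planned arm comparison uses the values.

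**2. How much data this concerns.** If the table in 5.5 governs, there are 5 fixed post-randomisation visits. The ceiling is 200 × 5 = 1,000 patient-visits before the projected 30% attrition; the 140 projected completers alone give 140 × 5 = 700. If the visit text governs, the only draw routine for everyone is month 12, at most 200 × 1 = 200. Sodium is in none of the post-randomisation visit lists. The Baseline visit 1 list in 5.6.2 omits potassium and sodium, although the safety list in 5.6 includes both.

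**3. What reliance on recording could cost (illustration).** The documents give no laboratory event rate, recording rate or standard deviation, so there is no figure of the plan's own to reproduce on this point. The rates below are assumptions. Two-sided 5%, n per arm, p̄ the mean of the two rates:

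power = Φ{ [|p1 − p2| − 1.96 √(2p̄(1 − p̄)/n)] / √([p1(1 − p1) + p2(1 − p2)]/n) }

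For 10% versus 25% with n = 100: p̄ = 0.175, √(2 × 0.175 × 0.825/100) = 0.0537 and √((0.09 + 0.1875)/100) = 0.0527. This gives (0.15 − 0.1053)/0.0527 = 0.85 and Φ = 0.80.

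| Assumed situation | Rates compared | n = 100, normal | n = 100, Fisher exact | n = 70, normal |
|---|---|---|---|---|
| All events counted from values | 10% vs 25% | 80% | 76% | 65% |
| Half recorded in each arm | 5% vs 12.5% | 47% | 38% | 35% |
| A quarter recorded in each arm | 2.5% vs 6.25% | 25% | 14% | 19% |
| No true difference (20% in both), recorded 30% vs 60% of the time | 6% vs 12% | 32% false positive | 24% | 23% |

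With lower assumed rates, power is low even if every event is counted: 2% versus 5% gives 16% to 21%, and 5% versus 10% gives 20% to 27% (70 to 100 per arm).

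**4. What a comparison of the values could detect.** For a continuous value with 80% power, the detectable difference in SD units is (1.96 + 0.84) × √(2/n): 0.40 SD at 100 per arm and 0.47 SD at 70 per arm. This needs no assumption about event rates or recording.

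**The case against.** The strongest reply is that the values may not support the analysis. If the visit text governs, staff who know the arm decide who is tested at every visit except month 12. A comparison of those values then carries the same ascertainment bias as the adverse events. This stands, and it determines how the fix must be built.

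A second reply is that these harms are not invisible. An overnight hospitalisation is a serious event by definition (5.10), so severe cases depend less on judgement. Renal events are named for capture (5.7, 5.8), discontinuations due to adverse events are tabulated by arm, and the committee sees laboratory data. All true, but ordinary shifts in creatinine or potassium lack the protection that hospitalisation gives, and the committee reports are for oversight.

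A third reply is that the SAP is a modification adding secondary analyses, so its silence proves little. That has some force, but the Protocol's statistical section is silent too.

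A reader might also infer three things that the documents do not support:

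- That the arms are known to differ in renin-angiotensin blocker, diuretic or aldosterone antagonist exposure. Section 5.1 describes similar regimens, gives lisinopril the same starting and maximal dose in both arms, and offers diuretic and aldosterone antagonist as add-on steps to both. More exposure under the lower target is plausible but not documented.
- That a 15% creatinine rise or a potassium of 3.5 meq/L is a harm threshold. The first is an example of a small change, the second a replacement target.
- That 1,000 routine results will exist. That is a ceiling under one of two conflicting sources.

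**Conclusion.** The point holds as a gap in the safety analysis. The protocol singles out these tests and foresees the harms, but the plan followed as written leaves the values out of the arm comparison and relies on events and discontinuations that, hospitalised cases aside, are recorded with knowledge of the assignment.

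Its size is not established. The power figures are illustrations under assumed event and recording rates; they show the direction of the problem, not its amount in this trial. A reader might infer that an excess will be missed or a false one reported. The documents show only that the plan has no safeguard against either. The primary and secondary efficacy inferences are untouched. The change is worth making because it is cheap, not because the trial's conclusions depend on it.

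**What to change.** 1. Reconcile the chemistry row of the table in 5.5 with the visit text in 5.6.3 and 5.6.4, and the baseline laboratory list in 5.6.2 with the safety list in 5.6. Which schedule applied is for the sponsor to state.

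2. Add to SAP item 7, before database lock, a by-arm analysis of values already collected:
   - change from baseline in log creatinine or eGFR, and in potassium and sodium where measured, adjusted for the baseline value, with estimates and 95% confidence intervals;
   - the proportion per arm with a doubling of creatinine, or with potassium or sodium outside the laboratory's reference range, with 95% confidence intervals. A 15% creatinine rise may be shown descriptively.

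3. Base the main comparison on draws that were unconditional for everyone: month 12, which both sources support, and the other table visits only if confirmed as routine. If several visits qualify, use a repeated-measures model. Report the number tested per arm at each visit. Use clinically triggered draws only in a sensitivity analysis.

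The cost is SAP wording and a little programming. No new tests are proposed, so potassium or sodium can be analysed only as far as it was measured. If only month 12 is complete, precision will be limited, and the report should say so.
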